7.2. Adjustments for Covariates

The general adjustment strategy has been described in the CPMP SAP Version 5.

7.3. Handling of Dropouts or Missing Data

The missing data strategy has been described in the CPMP SAP Version 5.

7.4. Multiple Comparisons/Multiplicity

There is no plan to formally adjust for multiplicity.

7.5. Use of an “Efficacy Subset” of Participants

There are no plans to use a modified efficacy subset.

7.6. Participant Disposition

The summary of participant disposition has been described in the CPMP SAP Version 5.

7.7. Participant Characteristics

The summary of participant characteristics has been described in the CPMP SAP Version 5.

7.8. Treatment Compliance

Treatment percentage of compliance will be calculated as:

$$\frac{\text{Total pills taken} * 100}{\text{Total pills expected}} \%$$

with total pills taken calculated by total pills dispensed minus total pills returned. A patient is considered to be compliant for a given period if this percentage is between 80% and 120%. Treatment compliance will be assessed at Visits 5 and 7 (and early discontinuation visit, if applicable); at Visits 4 and 6, the investigational product will not be returned to the site. Treatment compliance will be reported for the 8 weeks of the treatment period (Visit 3 to Visit 7). The percentage of patients who are compliant with study drug will be summarized by treatment group. For patients who discontinue early, time after the penultimate visit will be excluded for calculation of treatment compliance. For example, if the patient discontinued early at Visit 6, treatment compliance will be derived only from data collected through Visit 5. Comparisons between treatment group for treatment compliance will be performed using a Fisher's Exact test. Listings for treatment compliance of individual patients by treatment period will also be provided.

Depending on the level of observed treatment compliance, and where appropriate, sensitivity analyses of primary endpoints may be conducted by excluding patients with poor treatment compliance.

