1.3. Schedule of Activities (SoA)

This SoA shows visits and procedures unique to the ISA H0P-MC-OA05 for LY3857210. Please refer to the Master Protocol CPMP and the OA DSA CPMP(1) SoAs for additional information.

	Screening		Randomization to ISA	Double-Blind Treatment				F/U	Notes	
	V1	V2		V4	V5	V6	V7			
Study Week	Up to -6 month	-10 to -7 days for most participants	0	2	4	6	8		+2	
Visit Window (days)				±3					±3	
Confirm ISA inclusion and exclusion criteria	X	X	X							
Physical examination			X	X		X	X	X		Physical examination (see Section 8.2.1). Complete physical examination, including targeted examination specified below, should be performed at V3 and V801 or ED. Targeted physical examination for skin, gastrointestinal tract, mammary gland in males, and lymph nodes should also be performed at V5 and V7.
Neurological assessment			X	X	X	X	X	X		See Section 8.2.1.
Prespecified OA medical history			X							Includes diagnosis and symptom onset date.
Vital signs			X	X	X	X	X	X		At V3, vitals should be taken predose. Pulse rate, respiratory rate, blood pressure, and temperature taken with participant in a sitting position.
Concomitant medication									X	See footnote a.
AE									X	See footnote a.

	Screening		Randomiza tion to ISA	Double-Blind Treatment				F/U	Notes	
	V1	V2		V4	V5	V6	V7			
Study Week	Up to -6 month	-10 to -7 days for most participants	0	2	4	6	8		+2	
Visit Window (days)				±3				±3		
ECG (single)				X		X	X			
Placebo response video training (participant)		X								Should view at the beginning of V2.
Study intervention administration			X	X	X	X				See Section 6.1. Participant should be instructed NOT to take study intervention on the day of V7.
Dispense study intervention to participant			X	X	X	X				
Participant returns unused study intervention				X	X	X	X	X		Participant to bring study intervention to every visit.
Intervention compliance				X	X	X	X	X		
Scales, Questionnaires, and Outcome Measures										

CCI

C-SSRS Since Last Visit								X	See footnote a.
Self-Harm Supplement form								X	See footnote a.
Self-Harm Follow-Up form								X	See footnote a. Complete 1 form for each event identified on the Self-Harm Supplement form.
NRS for pain								X	See footnote a. Review eDiary compliance.

	Screening		Randomiza tion to ISA	Double-Blind Treatment				F/U	Notes
	V1	V2		V4	V5	V6	V7		
Study Week	Up to -6 month	-10 to -7 days for most participants	0	2	4	6	8		+2
Visit Window (days)				±3				±3	

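### SAP 7.8 and the protocol disagree on product return and compliance checks at Visits 4 and 6, and the SAP rule for early discontinuers leaves the planned discontinuation-visit count out of the compliance percentage.

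*SAP*

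**What the plan says.** SAP 7.8 defines compliance as pills taken (dispensed minus returned) over pills expected, and calls a participant compliant between 80% and 120%. On timing it says: "Treatment compliance will be assessed at Visits 5 and 7 (and early discontinuation visit, if applicable". It adds that "at Visits 4 and 6, the investigational product will not be returned to the site".

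For those who stop early, the rule is "For patients who discontinue early, time after the penultimate visit will be excluded for calculation of treatment compliance", with the example that "if the patient discontinued early at Visit 6, treatment compliance will be derived only from data collected through Visit 5".

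The percentage compliant is summarised by arm and compared with Fisher's exact test. The section also plans that "Listings for treatment compliance of individual patients by treatment period will also be provided", and that "sensitivity analyses of primary endpoints may be conducted by excluding patients with poor treatment compliance" where the observed compliance makes this appropriate.

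The protocol differs on timing. Section 6.4 has compliance assessed at each visit, by questioning and by counting returned capsules, and has start and stop dates recorded in the CRF. The Schedule of Activities (section 1.3) has a row "Participant returns unused study intervention" and a compliance row, each with five marks that fit Visits 4 to 7 and the early discontinuation visit. Its note tells participants to bring product to every visit, and section 4.1 says the same of bottles at Visits 4 through 7.

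**The concern.** There are two separate problems.

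First, the SAP and the protocol describe different site procedures at Visits 4 and 6. A capsule count either exists at those visits or it does not, and the documents do not show which schedule was followed. The visible SAP text does not present the difference as a deliberate change from the protocol.

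Second, the SAP plans a count at the discontinuation visit and then excludes the interval that this count would close. For early discontinuers the percentage therefore cannot show adherence in the period just before they left. For some of them there may be no usable count at all.

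At stake are the reported percentage compliant by arm, the Fisher's exact test on it, and the set excluded from the sensitivity analysis if that analysis is run.

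**Working it through.** There is no figure in the plan to reproduce. The check sets the rules side by side and applies the SAP's own formula.

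**Inputs.** Up to about 125 randomized and about 80% expected to complete (protocol 9.5, SAP 6.2). Visits 3 to 7 at Weeks 0, 2, 4, 6 and 8 (protocol 1.3), taken here as days 0, 14, 28, 42 and 56. Daily dosing (protocol 6.1); the number of capsules per day cancels.

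**Number who could be affected.** 125 × (1 − 0.80) = 25.

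**What the SAP rule leaves, if nothing is returned at Visits 4 and 6.**

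| Leaves | Penultimate visit | Return count there | Data entering the percentage |
|---|---|---|---|
| By Visit 4 | Visit 3 | none | none: all dosing time is excluded |
| After Visit 4, by Visit 5 | Visit 4 | none | none apparent |
| After Visit 5, by Visit 6 | Visit 5 | yes | Visits 3 to 5 (the SAP's example) |
| After Visit 6 | Visit 6 | none | Visits 3 to 5, the last count available |

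Under the protocol's schedule with the same exclusion, only the first row has no value. The others lose only the last interval.

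**Split of the 25.** The documents do not give dropout timing, so this is assumption only. At a constant hazard, 125 × (1 − 0.8^(4/8)) = 13.2 would leave by Visit 5. If 30% or 70% of dropouts occurred by Week 4, the number would be 0.30 × 25 = 7.5 or 0.70 × 25 = 17.5.

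**Direction of error.** These are constructed cases with discontinuation at Visit 6 (day 42), where both schedules cut at Visit 5.

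- 28 of 28 doses to Visit 5, then 5 of 14 spread out with the last on day 42. SAP rule: 28/28 = 100%, compliant. With the discontinuation count: (28 + 5)/42 = 78.6%, not compliant.
- 20 of 28 to Visit 5, then 14 of 14. SAP rule: 20/28 = 71.4%, not compliant. With the discontinuation count: (20 + 14)/42 = 81.0%, compliant.
- 28 of 28, then 5 consecutive doses and a permanent stop on day 33. SAP rule: 100%. To the stop date: 33/33 = 100%. To the visit date: 33/42 = 78.6%. Here the class depends only on the denominator.

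**How easily the class changes.** After perfect adherence to Visit 5, falling below 80% by day 42 takes 9 missed doses of 14 (34/42 = 81.0% with 8 missed; 33/42 = 78.6% with 9). At day 35 it cannot happen, since 28/35 = 80.0% is still within the band.

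**The case against.** The case on the other side has force in several places.

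- **Evidence for the visit conflict.** Bringing bottles is not the same as returning product, so the Schedule of Activities note and section 4.1 do not contradict the SAP by themselves. The column alignment of the extracted schedule is also imperfect. Both points stand. The firm conflict is protocol 6.4 against SAP 7.8; the other places only support it.
- **The exclusion is not a contradiction.** A reader might infer that SAP 7.8 contradicts itself by planning a discontinuation-visit assessment and then cutting at the penultimate visit. It does not, strictly: the count can still appear in the individual listings. What stands is that, on the SAP's own example, the count does not enter the percentage.
- **Counts by interval.** If each dispensing is a separate supply, product returned at discontinuation might be attributed to the earlier interval, giving a value to some participants shown above without one. Packaging is not described, so this remains open. It would not help those leaving by Visit 4, who have no time left to score.
- **The exclusion has a purpose.** It avoids counting days after a permanent stop as missed doses. The third case above shows why that matters. A participant who took nothing after Visit 5 scores 28/42 = 66.7% to the visit date but 28/28 = 100% to the stop date, as under the SAP. This objection is met by the choice of denominator, not by dropping the interval.
- **Missing values.** Section 7.8 does not say how participants without a value enter the percentage or the test. A reader might infer that the plan has no rule. The documents do not support that, because SAP 7.3 says "The missing data strategy has been described in the CPMP SAP Version 5", and that document is not available here.

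**Conclusion.** The concern holds, at low severity. SAP 7.8 and protocol 6.4 disagree on whether compliance is assessed and product returned at Visits 4 and 6. Separately, the penultimate-visit rule keeps the planned discontinuation-visit count out of the percentage. If the SAP schedule was followed, those leaving by Visit 5 appear to have no usable count, subject to the open question on supplies, and later leavers are scored only through Visit 5.

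Up to about 25 of 125 participants could be affected, which assumes the expected 20% dropout. The timing of dropout, the number reclassified and any difference between arms are unknown. The error can go in either direction.

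A reader might infer that the efficacy result is at risk. The documents do not support that. Completers are unaffected, the primary analysis does not use compliance, SAP 7.1 defines the key secondary treatment condition without regard to adherence, and the compliance-based sensitivity analysis is optional.

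**What to change.** 1. Reconcile the return and assessment visits between SAP 7.8 and protocol 1.3, 4.1 and 6.4, and state the schedule actually followed.
2. For early discontinuers, replace the penultimate-visit exclusion with the capsule count already planned at the discontinuation visit. Divide by the doses expected from first dose to the recorded stop date, so that days after a permanent stop are not counted as missed. Report early stopping separately.
3. Say in 7.8, by cross-reference if CPMP SAP Version 5 already covers it, how participants with no value enter the percentage and Fisher's exact test.

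The cost is SAP wording and one derivation. The count and the stop date are already planned, and no Visit 4 or 6 count is needed. Reported compliance may shift slightly either way. Participants with no return at discontinuation, such as those lost to follow-up, would still have no value and fall under the missing-data rule in force.

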7.9. Concomitant Therapy and eCOA Compliance

The summary and reporting of concomitant therapy and eCOA compliance has been described in the CPMP SAP Version 5. No additional covariates will be considered in the models of weekly rescue medication use.

Concomitant therapy will be reported separately for the 8 weeks of the double-blind period and for the entire 10-week study period.

7.10. Efficacy Analyses

7.10.1. Primary Outcome and Methodology

The analysis of the primary outcome has been described in the CPMP SAP Version 5, and it constrains baseline means to be equal between arms. CCI

As noted in Section 5.1, endpoint for the primary analysis is defined as 8 weeks post initial treatment administration.

Calculation of the weekly/bi-weekly time intervals used for analysis of weekly/biweekly mean scores from the eCOA device will follow the algorithm described in the CPMP SAP Version 5, Section 6.12.1, except that the end of the final interval will be determined based on the last VAS collection date, or the last scheduled visit start date if VAS results are missing for the last scheduled visit.

7.10.2. Additional Analyses of the Primary Outcome

The text 'CCI' is displayed in a large, bold, red font. It is positioned on a solid black rectangular background. The letters are slightly shadowed, giving them a 3D appearance.

Descriptive statistics of primary outcome variables by demographics, disposition, disease characteristics, and treatment administration may be summarized by ISA, in order to examine the population homogeneity assumption between ISAs.

7.10.3. Secondary Efficacy Analyses

Secondary efficacy analyses common to all ISAs within CPMP have been described in the CPMP SAP Version 5. Unless otherwise specified, the time point for secondary endpoint measurements is the same as that for the primary endpoint. Study OA05 will also consider the following secondary analyses.

The Western Ontario and McMaster Universities Osteoarthritis Index (Bellamy 2005) is a validated instrument that is extensively used to evaluate the response to medications for the treatment of osteoarthritic pain. The WOMAC® version LK3.1 will be administered according to the Schedule of Activities.

This 24-question WOMAC® and its subscales are described in [Table OA05.7.1](#).

Table OA05.7.1. WOMAC Subscales and Numbers of Questions

Dimensions/Subscales	Number of Questions
pain	5
stiffness	2
physical function	17

Abbreviation: WOMAC = Western Ontario and McMaster University Arthritis Index.

The participants will record their responses using a 0 to 4 Likert scale for each question:

- 0 = no pain (or stiffness or difficulty), and
- 4 = extreme pain (or stiffness or difficulty).

The scores for each subscale will be calculated by summing the scores of the questions in the respective subscale for each participant at each time point.

The range of possible scores for each subscale is pain = 0 to 20, stiffness = 0 to 8, and physical function = 0 to 68.

7.10.3.1. Key Secondary Analysis

A Bayesian longitudinal MMRM analysis will be performed to evaluate the change from baseline to each postbaseline visit up to Week 8 and separately up to Week 10 for the WOMAC® pain subscale, physical function subscale, and stiffness subscale. The model will utilize the cLDA model so that a common mean is estimated at baseline. More details on this approach are provided in the CPMP SAP Version 5.

Information included in the model is described in [Table OA05.7.2](#).

Table OA05.7.2. Bayesian Longitudinal MMRM Analysis Information

Categorical factors	
 • the interaction of treatment and time point (constrained to estimate a common mean at baseline across treatments) • average baseline pain severity category (baseline NRS < 7, baseline NRS ≥ 7) • pooled investigative site
Continuous covariates	
 • none

Abbreviations: MMRM = mixed-effect model for repeated measures; NRS = numeric rating scale.

7.10.3.2. Other Secondary Analysis

The proportion of participants in each treatment group meeting prespecified binary response thresholds (30%, 50%, and 70%) will be calculated for each postbaseline time point and will be used to compare treatment groups for WOMAC® pain and physical function subscales.

A Bayesian pseudo-likelihood-based categorical repeated measures model will be used to estimate the proportion of participants in each treatment group meeting the prespecified threshold for each postbaseline time interval up to Week 8 and separately up to Week 10. These estimates will be used to compare treatment groups. More details on this approach are provided in the CPMP SAP Version 5.

The model will include the categorical and continuous covariates described for the key secondary analysis.

In addition, time to first treatment response from baseline based on the prespecified binary thresholds above will be assessed. Analyses will be conducted according to the time to event analyses specified in the CPMP SAP Version 5.

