5.2. Secondary Objectives

Secondary objectives applicable to all ISAs are listed in the Study CPMP SAP Version 5.

The key secondary objective for Study OA05 is to evaluate whether LY3857210 is superior to placebo in reducing pain as measured by the mean change from baseline assessment to Week 8 for pain intensity measured by the WOMAC® pain subscale.

Additional secondary endpoints specific to Study OA05 are listed in [Table OA05.5.1](#).

Table OA05.5.1. Additional Secondary Endpoints Specific to Study H0P-MC-OA05

Objective	Endpoint Measure
Other Secondary	
Efficacy of LY3857210 versus placebo for overall improvement	Overall improvement up to 10 weeks as measured by the Patient Global Impression of Change
Efficacy of LY3857210 versus placebo	
Mean change from baseline to endpoint on the WOMAC® stiffness and physical function subscaleProportion of participants with reduction from baseline greater than or equal to 30%, 50%, and 70% on the WOMAC® pain subscale at each time pointProportion of participants with reduction from baseline greater than or equal to 30%, 50%, and 70% on the WOMAC® physical function subscale at each time point

Abbreviation: WOMAC = Western Ontario and McMaster University Arthritis Index.

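### Read alone, SAP 7.10.3.2 gives the WOMAC responder model no baseline WOMAC term; adding one, with standardised proportions, is cheap, but the precision gain is usually small

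*SAP*

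**What the plan says.** SAP 5.2 lists, among the other secondary endpoints, the proportion of "participants with reduction from baseline greater than or equal to 30%, 50%, and 70% on the WOMAC® pain subscale", and the same for physical function. SAP 7.10.3.2 analyses these with a Bayesian pseudo-likelihood categorical repeated measures model, which "will be used to estimate the proportion of participants in each treatment group meeting the prespecified threshold for each postbaseline time interval". On covariates it says: "The model will include the categorical and continuous covariates described for the key secondary analysis".

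The key secondary analysis (SAP 7.10.3.1) is a Bayesian longitudinal MMRM of the continuous scores: "The model will utilize the cLDA model so that a common mean is estimated at baseline". Table OA05.7.2 lists its categorical factors as treatment by time point (constrained at baseline), "average baseline pain severity category (baseline NRS < 7, baseline NRS ≥ 7"), and pooled investigative site. The entry for continuous covariates is none.

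Two sentences point elsewhere. On the responder model: "More details on this approach are provided in the CPMP SAP Version 5". On covariates in general (SAP 7.2): "The general adjustment strategy has been described in the CPMP SAP Version 5". That document was not supplied.

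**The concern.** The absence of a continuous covariate is deliberate and sensible in the key secondary model. A cLDA puts the baseline score into the response vector, so baseline WOMAC informs the treatment contrast through the within-participant covariance. The responder model has no baseline response, because a percent reduction exists only after baseline. The cLDA route is therefore closed, and borrowing the covariate list borrows an empty continuous row. The baseline constraint in the treatment-by-time factor has no function there either. What remains is a two-level category from a different instrument, plus site.

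At stake is some precision in the responder differences. The OA05 text also does not say whether model-based group proportions are averaged over participants or evaluated at covariate means, and this matters more once a prognostic continuous covariate is in a logistic-type model.

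**Working it through.** **Inputs from the documents.** Up to about 125 randomised and about 80% completing (SAP 6.2), so 125 x 0.80 = 100 completers. Score ranges are 0 to 20 for pain and 0 to 68 for physical function (SAP 7.10.3). The plan states no power or precision for this analysis, so there is no figure to reproduce.

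**Assumed inputs.** None of these is in the documents, and the allocation ratio is redacted.
- Pain: baseline mean 11, SD 3; Week 8 placebo mean 7.5, SD 4.5; effect 1.5.
- Physical function: baseline mean 36, SD 11; Week 8 placebo mean 26, SD 15; effect 5.
- Baseline-endpoint correlation r of 0.1, 0.3, 0.5 or 0.7; allocation 1:1 or 2:1; correlation 0.5 between baseline WOMAC and the latent score behind the NRS category; six sites with no true site effect.

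**Step 1: why the gain is often near zero.** A participant responds at threshold c if the Week 8 score is at most (1 - c) x baseline. Under a linear regression of Week 8 on baseline, the margin for response changes with each baseline point by

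(1 - c) - r x SD8/SD0.

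For pain, SD8/SD0 = 4.5/3 = 1.5, so the association vanishes at r = (1 - c)/1.5, which is 0.47, 0.33 and 0.20 for the 30%, 50% and 70% thresholds. For function, 15/11 = 1.36 gives 0.51, 0.37 and 0.22. Below these values higher baseline favours response; above them it works against response. Baseline already sits in the denominator of the outcome, so the gain from adding it is not monotone in r.

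**Step 2: simulated efficiency.** 48 settings, 3,000 trials each, n = 100. Each trial was fitted with NRS category and site, with and without the baseline score, and the Week 8 difference was standardised over participants. Two models were used: a Week 8 logistic model, and a pooled logistic model over four assumed visits. Relative efficiency is variance without the term divided by variance with it.

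| r | Relative efficiency | Median |
|---|---|---|
| 0.1 | 0.98 to 1.08 | not tabulated |
| 0.3 | 0.98 to 1.03 | 1.00 |
| 0.5 | 0.99 to 1.07 | 1.01 |
| 0.7 | 1.03 to 1.22 | 1.12 to 1.13 |

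The median over all settings is 1.02, and 16 or 17 of 48 settings (by model) fall below 1.00. With 10,000 trials the setting with function, r = 0.7 and 70% threshold gives 1.150 and 1.158 in the two models. Settings close to the vanishing points of Step 1 give 0.990 to 0.996 (pain 0.3 at 50%; function 0.5 at 30%; function 0.3 at 70%). Power changes by -0.3 to +4.3 percentage points.

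A simpler simulation (pain only, one visit, no site term, Week 8 SD 4, mean reduction 3 on placebo and 4 on drug) agrees. The SE runs from 0.5% larger to 2.4% smaller at r = 0.2 to 0.6, and is 3.3% to 10.6% smaller at r = 0.8.

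**Step 3: chance imbalance is the same gain.** At 1:1 the SE of the baseline pain imbalance is 3 x sqrt(1/50 + 1/50) = 0.6, so a 1-point imbalance is 1/0.6 = 1.67 SE (probability 0.096, both directions). Over the grid it moves the responder difference by -4.6 to +3.7 percentage points without the term and by at most 0.5 with it. The worst case is 0.5 to 0.6 of the SE of the difference. The variance share this implies is (0.5/1.67)^2 = 0.09 to (0.6/1.67)^2 = 0.13, hence a relative efficiency of 1/(1 - 0.09) = 1.10 to 1/(1 - 0.13) = 1.15. That is about the gain already seen at the top of the grid.

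**Step 4: why standardise.** Adding the term leaves the mean standardised difference unchanged within 0.002. It does move the conditional odds ratio: in the simpler simulation (r = 0.8, 70%, 1:1) the log odds ratio goes from 0.606 to 0.827 while the risk difference stays at 0.054. An active-arm proportion taken at covariate means is off by up to 2.1 points on average without the term and up to 6.8 with it. Standardised proportions agree with the observed ones within 0.005.

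**The case against.** The strongest objection is that the absence is not established. OA05 is a supplement, and it sends the reader to CPMP SAP Version 5 both for this model and for covariate adjustment generally. A reader might infer that the trial will certainly analyse WOMAC response without baseline WOMAC. The documents do not support that; they support only a reading of the OA05 text alone.

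A reader might also infer that the responder comparison is biased or invalid. It is not: randomisation protects it whether or not the term is present, apart from assumptions about missing data. With about 20% not completing, those assumptions matter, and dropout was not simulated.

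A third tempting reading is that protection against chance imbalance is a benefit on top of precision. Step 3 shows that it is the same quantity, and the planned SE already covers that variation.

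It is also fair to say that a change which is neutral or slightly negative in about a third of settings does not show the written choice to be wrong, and that much of the need for standardisation comes from the added term itself. The opening sentence of SAP 7.10.3.2 can be read as reporting observed proportions, which need no covariate convention. What stands is narrower: the covariate list was written for a model that uses baseline WOMAC by another route, and the data to replace that route are already collected.

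**Conclusion.** The point holds as a cheap improvement, not as an error in the plan. On the OA05 text alone, the responder model loses the baseline WOMAC information that the cLDA uses. Restoring it is worth roughly nothing at correlations of 0.3 to 0.5 and about 1.03 to 1.2 in relative efficiency at 0.7. The median of 1.02 equals about 2 extra completers per 100.

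These sizes rest on assumed scores, correlations, allocation, sites and visits. The planned Bayesian pseudo-likelihood model was not simulated. The stake is low: these are other secondary endpoints in a proof-of-concept study, no decision rule in the unredacted text rests on them, and SAP 7.4 states: "There is no plan to formally adjust for multiplicity". Time to first response is outside this point.

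**What to change.** If CPMP SAP Version 5 already puts the matching baseline score in this model and states how proportions are formed, cite that section in SAP 7.10.3.2; the analysis does not change. Otherwise add to SAP 7.10.3.2:

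> The responder model will also include the continuous baseline score of the subscale being analysed. In each posterior draw, response at each time point will be predicted for every participant under each treatment and averaged over the observed baseline distribution; group proportions and their difference will be reported from these averages.

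The cost is one model term and one standardisation step, with no new data. When baseline is not prognostic, about 1% of efficiency is lost (1.5% in the worst simulated setting; allow 2%). With few 70% responders the loss in the planned model could be larger.
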